Appendix 2: Study Procedures Timeline

Time	Activity	Control Group	Intervention Group
Day 0	Screening Consent Baseline Appointment	X	X
Day 1 – Days 7-15	Home BP measured and returned via text message	X	X
Days 7-15 – Day 18	Participants randomized; Pharmacists review home BP values, contact participants	X	X
Day 18 – 6 Months	Participants text home BP values 3 days per month Pharmacists monitor BP, adjust treatment as needed		X
6 Months	Participants return to clinic for appointment	X	X
6 Months – 12 Months	Participants text home BP values 3 days per month Pharmacists monitor BP, adjust treatment as needed		X
12 Months	Participants return to clinic for appointment	X	X

Appendix 3: REDCap Screening Form

Page 1

Screening

Record ID

.....

Screening Information

Clinic

- UIHC
- IRL
- North Liberty
- Scott Blvd (IC)
- River Crossing (Riverside)
- Muscatine (Muscatine)

Date

.....

Screening Intern

- [name]
- [name]
- [name]
- [name]
- [name]
- [name]

Patient Information from Epic (double check with patient)

Patient First Name

.....

Patient Last Name

.....

MRN

.....

Age

(Patient must be 21 - 100 to be eligible.)

Patient Zip Code

.....

Patient RUCA Code

(RUCA code must be ≥ 4 to be eligible.)

Blood Pressure Information

At least 2 elevated BP measurements in past 18 months?

Yes

No

(Patient must have at least 2 elevated BP measurements within past 18 months, at least 2 weeks apart from each other, to be eligible.)

Elevated BP values taken today do count!

First Elevated SBP

.....

First Elevated DBP

.....

Date of First Elevated BP

.....

Second Elevated SBP

.....

Second Elevated DBP

.....

Date of Second Elevated BP

.....

Information from Patient

Is female patient currently pregnant, or planning to become pregnant in next 12 months?

Yes

No

Patient is male

(Patients currently or planning to become pregnant are NOT eligible.)

Prisoner Status

Yes

No

(Patients with prisoner status are NOT eligible.)

Does the patient have a condition that prevents them from providing their own written informed consent?

Yes

No

(Patients who cannot provide their own consent are NOT eligible.)

Arm circumference (cm)

(Patients with arm circumference greater than 50 cm (20 in) are NOT eligible.)

Preferred Language

English

Spanish

01/02/2020 12:34pm

projectedcap.org

 REDCap[®]

idential

Patient Eligibility

Is Patient Eligible?

Yes

No

Appendix 5: Baseline REDCap Form

Page 1

Baseline Data

Record ID _____

Date of Baseline Measures _____

Research Blood Pressure Measurements:

--Prepare the Participant--

- *No smoking 20 minutes prior to BP measurement
- *Remove all clothing that covers the location of cuff placement
- * Sit comfortably in a chair, with back supported, legs uncrossed and flat on floor, arm supported at level of the heart on table, palm facing upward
- *Sit for at least 5 minutes before first measurement; relax as much as possible

--Cuff Measurement--

- * Choose cuff that fits arm circumference you previously measured. If arm measurement falls on number that is specified for 2 cuffs, both cuffs should be placed on arm sequentially and the cuff for which the INDEX arrow that is marked on the cuff best falls within the range bar should be chosen

--Cuff Placement--

- *Do not allow a sleeve to form a tourniquet on the arm
- *Palpate the brachial artery in the antecubital fossa and place the ART arrow that is marked on the midline of the bladder of the cuff so that it is over the arterial pulsation of the participant's bare arm
- * The lower end of the cuff should be 1/2 to 1 inch above the inner side of the elbow joint
- *The middle of the cuff should be at the level of the right atrium
- * Place the cuff snugly around the bare upper arm so that you can only insert one finger between the cuff and the arm

--BP Measurement--

- *Use the Omron HEB-907-XL
- *Tell the participant you will be taking 3-4 measurements and that neither of you should talk during the measurement time
- *Take first measurement and record (this value will be ignored). Wait 60 seconds before taking next measurement
- *Take second measurement and record. Wait 60 seconds before taking next measurement
- *Take third measurement and record. If 2nd and 3rd values are more than 4 mmHg apart, take a 4th reading.
- *The two nearest values (of 2-4) will be averaged. If the average value is less than 145 or 95, the person NOT eligible to continue with the study. Thank them for their time.

If you get an error message at any point, start the sequence over!

1st Blood Pressure (this value is ignored)

Baseline SBP #1

Baseline DBP #1

2nd Blood Pressure

Baseline SBP #2

Baseline DBP #2

(If average BP value is less than 145 or 95, the patient is NOT eligible.)

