3.1 Inclusion Criteria

- English or Spanish speaking males and females.
- 21 – 100 years of age.

- Clinic measured blood pressure of ≥ 145 mmHg or ≥ 95 mmHg at two previous clinic visits or one previous clinic visit and on the day of enrollment. Previous clinic visit BPs must be within the past 18 months and measured at least 2 weeks apart from each other.
- Lives in a zip code that is scored as a 4-10 on the Rural-Urban Commuting Area (RUCA) Codes.

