 - Repeat this two more times.
 - The average of the 2nd and 3rd readings will be used as the research BP for this visit.
 - If the 2nd and 3rd BP values are more than 4 mmHg apart, a 4th value will be obtained and the two nearest values will be averaged. This will serve as the research BP for that visit.

IF YOU GET AN ERROR MESSAGE AT ANY POINT, START THE SEQUENCE OVER.

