**3rd Blood Pressure**

Baseline SBP #3

Baseline DBP #3

(If average BP value is less than 145 or 95, the patient is NOT eligible.)

4th Blood Pressure (only needed if the 2nd and 3rd measurements are more than 4 mmHg apart.)

Baseline SBP #4

Baseline DBP #4

(If average BP value is less than 145 or 95, the patient is NOT eligible.)

Patient Contact Information

Phone Number

Permission to Text the Above Number

yes
 no

Email Address

Street Address

(needed for compensation checks)

City, State, Zip

(needed for compensation checks)

Distance from participant's home to clinic (miles)

(This field can be calculated after the appointment.)

Additional Contact Information

This person will only be contacted if we have trouble reaching the participant. We will not tell the contact person details about the study, just that the participant is enrolled in a research study at the University of Iowa and has listed them as someone who will know how to reach them.

Relationship to Participant

Contact Name

Contact Phone Number

Demographic Information

Race

- American Indian or Alaska Native
- Asian
- Black or African American
- Native Hawaiian or Other Pacific Islander
- White
- Multiracial
- Other

Ethnicity

- Hispanic
- Non-Hispanic
- Unknown

If other, please specify

Sex

- Male
- Female
- Other

If other, please specify

Insurance

- Private (Insurance through employer or self-purchased)
- State insurance/Medicaid
- Federal insurance/Medicare
- Uninsured

Level of Education	 < High school  High school diploma or GED  Some college or trade school  Associate's degree  Bachelor's degree  Master's degree  Doctorate or Professional Degree  Trade license or certification
--------------------	---

Marital Status	 Never married  Married  Living as married  Divorced or separated  Widowed
----------------	---

Smoking Behaviors

Smoking Status	 Never smoked  Current smoker  Ex-smoker
----------------	---

Number of Years Smoked

Number of Cigarettes Smoked Per Day

Years Since Quit Smoking

Smokeless Tobacco Behaviors

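### Appendix 5's baseline stop rule, read literally, requires both SBP ≥145 and DBP ≥95, whereas Section 3.1 requires only one; the two must be reconciled in a single edit

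*Combined protocol and SAP*

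**What the plan says.** **Entry rule.** Section 3.1 asks for "Clinic measured blood pressure of ≥ 145 mmHg or ≥ 95 mmHg at two previous clinic visits or one previous clinic visit" plus the day of enrollment. The synopsis and Section 4.2 give the same rule. There are two routes in: two previous visits, or one previous visit and the enrollment day. On either route, one raised component suffices.

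**Screening form (Appendix 3).** It asks: "At least 2 elevated BP measurements in past 18 months". It adds: "Elevated BP values taken today do count". A same-day value may therefore be one of the two, but need not be. The form prints no numerical limit for what counts as elevated.

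**Baseline procedure (Section 4.3.2).** "The average of the 2nd and 3rd readings will be used as the research BP for this visit", with a fourth reading if the second and third differ by more than 4 mmHg. The section excludes on arm circumference only and contains no blood pressure stop.

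**Baseline form (Appendix 5).** The measurement instructions end with: "If the average value is less than 145 or 95, the person NOT eligible to continue with the study". The intern is then told to thank the person for their time. A note under each of readings 2, 3 and 4 says: "If average BP value is less than 145 or 95, the patient is NOT eligible". The stop therefore appears four times.

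**The concern.** The form negates each limit but keeps the word 'or' between them. The opposite of meeting at least one limit is failing both, so the form's literal rule is not the complement of the entry rule. Someone raised on systolic pressure alone, or on diastolic pressure alone, meets the criterion in Section 3.1 and fails the form.

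The instruction is operative. Section 4.3.1 places the baseline measurements after consent, so an intern following the form literally ends the participation of a consented person. Among the data forms shown, this is the only one that prints 145 and 95. Three to five interns work across several clinics, and different interns could apply the two readings differently.

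What is at stake is the enrolled population. The primary outcome is SBP, and the literal rule would remove people whose only raised component is systolic. It would also lose consented people from a recruitment target of 420.

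**Working it through.** The plan gives no figure for this point, so there is nothing to reproduce. The check is one of logic.

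**Step 1. Write the two rules.** Let S be the average SBP and D the average DBP.
- Entry rule (Section 3.1): meets the limit if S ≥ 145 or D ≥ 95.
- Appendix 5, literal: not eligible if S < 145 or D < 95. Eligible therefore means S ≥ 145 and D ≥ 95.
- True complement of the entry rule: not eligible if S < 145 and D < 95.

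**Step 2. Compare on examples.**

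| Average BP | Meets entry limit | Passes form, literal | Passes form, complement |
|---|---|---|---|
| 160/100 | yes | yes | yes |
| 160/85 | yes | **no** | yes |
| 140/100 | yes | **no** | yes |
| 140/85 | no | no | no |
| 145/95 | yes | yes | yes |
| 145/94 | yes | **no** | yes |
| 144/95 | yes | **no** | yes |

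The disagreement is exactly the set with one raised component.

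**Step 3. Compare on a full grid.** For whole-number SBP 100–220 and DBP 50–130 there are 121 × 81 = 9,801 combinations.
- S ≥ 145 and D < 95: 76 × 45 = 3,420.
- S < 145 and D ≥ 95: 45 × 36 = 1,620.
- The literal form disagrees with the entry rule at 3,420 + 1,620 = 5,040 combinations; the complement disagrees at 0.

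These are combinations of values, not proportions of patients.

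**Step 4. Walk one person through.** Previous visit 160/82; research average today 158/84. If the research average is the enrollment-day reading that Section 3.1 has in mind, this person qualifies (158 ≥ 145). The literal form stops them (84 < 95).

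**Step 5. Test the second route.** Someone raised at two previous visits, with a baseline average of 140/85, is admitted by Section 3.1 on history alone. Appendix 5 stops them under the literal reading and under the complement. Correcting the connective alone does not make the form match Section 3.1.

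**Step 6. Illustrative size, on assumptions only.** The documents give no blood pressure distribution. Assume bivariate normal baseline averages: SBP mean 145–155 (SD 15–18), DBP mean 80–90 (SD 10–12), correlation 0.4–0.6.

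Share stopped among those meeting the entry limit that day = 1 − P(both) / P(either), where P(both) = P(S ≥ 145) + P(D ≥ 95) − P(either).
- Lowest (SBP 145, SD 15; DBP 90, SD 12; correlation 0.6): P(S) = 0.500, P(D) = 0.338, P(either) = 0.577, P(both) = 0.262. Share = 1 − 0.262/0.577 = about 55%.
- Highest (SBP 155, SD 15; DBP 80, SD 10; correlation 0.4): P(S) = 0.748, P(D) = 0.067, P(either) = 0.752, P(both) = 0.063. Share = 1 − 0.063/0.752 = about 92%.

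This supposes that every intern applies the literal reading every time. It also ignores the earlier screening for raised readings.

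**The case against.** The strongest reply is that the phrase is shorthand. It speaks of one average value without naming SBP or DBP, and can be read as below the 145-or-95 entry limit, which is the correct complement. The governing rule is stated identically in three places, including the interns' own screening procedure in Section 4.2. That section also sends unsure interns to the clinic's medical staff, and Section 7 provides for training, monitoring and telephone support.

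This stands in part. A reader might infer that people raised on one component are in fact being turned away. The documents show only that they could be, if the form is followed literally. The safeguards lower that risk, but they leave in place an eligibility instruction with two readings that select different populations.

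Two further inferences go too far. A reader might suppose that the trial comparison is biased. It is not: the check is made on Day 0, before assignment (Section 4.1, Appendix 2), so it cannot act differently in the two arms. A reader might also take 55–92% as the expected loss. Those figures rest wholly on assumed distributions and universal literal application, so they show that the two readings can differ widely, not what happened.

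A last point against the worked example also stands. Section 3.1 refers to clinic-measured BP, while the form tests the research average. The documents do not say whether these are the same reading.

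**Conclusion.** The point holds as a conflict between an operative eligibility form and the protocol's inclusion criterion. Read literally, Appendix 5 demands both raised components where the synopsis and Sections 3.1 and 4.2 demand one, and nothing else in the documents corrects it. The consequence is for who is enrolled, for recruitment yield and for the population to which the result applies. The number of people affected is unknown and cannot be obtained from the documents.

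The logical finding needs no assumption beyond the literal reading. The claim that a given person meets Section 3.1 but fails the form also assumes that the research average counts as the enrollment-day reading. It would be too quick to conclude that changing the connective settles the matter, because either reading of the form makes a raised baseline-day average compulsory, including for those who qualify on two previous visits. The documents do not show which text reflects the intention, so one of them must change. It should be settled before the form is used further, because the form decides entry.

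**What to change.** Reconcile Appendix 5 with Section 3.1 in one edit:

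1. **Stop rule.** For the route of one previous visit plus the day of enrollment, replace the wording in the instruction and in all three reading notes with: *not eligible only if average SBP is below 145 AND average DBP is below 95*.
2. **Two-previous-visits route.** State whether any baseline-day check applies to people who already qualify in this way.
3. **Which reading counts.** State whether the enrollment-day value is the clinic BP or the research average.
4. **Screening form.** Print *≥145 systolic or ≥95 diastolic* beside the elevated fields in Appendix 3.
5. **If both limits were in fact intended**, change Section 3.1, Section 4.2 and the synopsis instead.

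A calculated average with an automatic flag in REDCap would be a useful option. The note under the second reading refers to an average before the third reading exists.

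The cost is a wording edit to two forms and a clarifying sentence in the protocol, with no added participants, visits or staff. If item 5 applies, the protocol text changes as well.

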**3rd Blood Pressure**

Baseline SBP #3

Baseline DBP #3

(If average BP value is less than 145 or 95, the patient is NOT eligible.)

4th Blood Pressure (only needed if the 2nd and 3rd measurements are more than 4 mmHg apart.)

Baseline SBP #4

Baseline DBP #4

(If average BP value is less than 145 or 95, the patient is NOT eligible.)

Patient Contact Information

Phone Number

Permission to Text the Above Number

yes
 no

Email Address

Street Address

(needed for compensation checks)

City, State, Zip

(needed for compensation checks)

Distance from participant's home to clinic (miles)

(This field can be calculated after the appointment.)

Additional Contact Information

This person will only be contacted if we have trouble reaching the participant. We will not tell the contact person details about the study, just that the participant is enrolled in a research study at the University of Iowa and has listed them as someone who will know how to reach them.

Relationship to Participant

Contact Name

Contact Phone Number

Demographic Information

Race

- American Indian or Alaska Native
- Asian
- Black or African American
- Native Hawaiian or Other Pacific Islander
- White
- Multiracial
- Other

Ethnicity

- Hispanic
- Non-Hispanic
- Unknown

If other, please specify

Sex

- Male
- Female
- Other

If other, please specify

Insurance

- Private (Insurance through employer or self-purchased)
- State insurance/Medicaid
- Federal insurance/Medicare
- Uninsured

Level of Education	 < High school  High school diploma or GED  Some college or trade school  Associate's degree  Bachelor's degree  Master's degree  Doctorate or Professional Degree  Trade license or certification
--------------------	---

Marital Status	 Never married  Married  Living as married  Divorced or separated  Widowed
----------------	---

Smoking Behaviors

Smoking Status	 Never smoked  Current smoker  Ex-smoker
----------------	---

Number of Years Smoked

Number of Cigarettes Smoked Per Day

Years Since Quit Smoking

Smokeless Tobacco Behaviors

Smokeless Tobacco Status	 Never used  Current user  Ex-user
--------------------------	---

Number of Years Using Smokeless Tobacco

Number of Snuffs/Dips/Chews Per Day?

Years Since Quit Smokeless Tobacco

Alcohol Behaviors

How often do you have a drink containing alcohol?	 Never  Monthly or less  2-4 times a month  2- 3 times a week  4 or more times a week
---	--

How many drinks containing alcohol do you have on a typical day when you are drinking?

1 or 2
 3 or 4
 5 or 6
 7, 8, or 9
 10 or more

Other Issues

Any History of These Issues

- Angina
- Anxiety
- Arthritis
- Asthma
- Cancer
- Chronic Kidney Disease
- Chronic Obstructive Pulmonary Disease (COPD)
- Coronary Artery Disease (CAD)
- Depression
- Diabetes
- Heart Failure
- Hyperlipidemia
- Liver Disease
- MI (heart attack)
- Peripheral Artery Disease (PAD)
- Seizures
- Stroke
- TIA (transient ischemic attack)
- None

Notes about Other Issues

Research intern who collected baseline data.

- [name]
- [name]
- [name]
- [name]
- [name]
- [name]

Appendix 6: BP Medications

Baseline BP Medications

Page 1

Record ID

BP Medication Code

BP Medication Name

Times/Day

(How many times is this medication taken per day?
(1, 2, 3, etc.))

Medication Notes

Research intern who obtained baseline medications.

- [name]
- [name]
- [name]
- [name]
- [name]
- [name]

Appendix 7: Drug Codes for Antihypertensive Agents

Diuretics – Class Code = 100

Code	Generic Name	Brand Names	Strengths Available
101	amiloride	Midamor	5 mg
102	amiloride/hydrochlorothiazide*	Moduretic	5/50 mg
103	bumetanide	Bumex	0.5 mg, 1 mg, 2 mg
104	chlorothiazide	Diuril	250 mg, 500 mg
105	chlorthalidone	Hygroton and others	25 mg, 50 mg, 100 mg
106	furosemide	Lasix	20 mg, 40 mg, 80 mg
107	hydrochlorothiazide	Hydrodiuril & others	12.5 mg, 25 mg, 50 mg
108	triamterene/hydrochlorothiazide*	Dyazide, Maxide	37.5/25 mg, 50/25 mg, 75/50 mg
109	indapamide	Lozol	1.25 mg, 2.5 mg
110	metolazone	Mykrox, Zaroxolyn	2.5 mg, 5 mg, 10 mg
111	polythiazide	Renese	1 mg, 2 mg, 5 mg
112	spironolactone/hydrochlorthiazide*	Aldactazide	25/25 mg, 50/50 mg
113	torsemide	Demadex	5 mg, 10 mg, 20 mg, 100 mg
114	triamterene	Dyrenium	50 mg, 100 mg
115	Ethacrynic acid	Edecrin	25 mg

* list specific strength of each ingredient

Beta Blockers – Class Code = 200

Code	Generic Name	Brand Names	Strengths Available
201	acebutolol	Sectral	200 mg, 400 mg
202	atenolol	Tenormin	25 mg, 50 mg, 100 mg
203	betaxolol	Kerlone	10 mg, 20 mg
204	bisoprolol	Zebeta	5 mg, 10 mg
205	metoprolol tartrate	Lopressor	25 mg, 50 mg, 100 mg
206	metoprolol succinate (extended release)	Toprol XL	25 mg, 50 mg, 100 mg, 200 mg
207	nadolol	Corgard	20 mg, 40 mg, 80 mg, 120 mg, 160 mg
208	penbutolol	Levatol	20 mg
209	pindolol	Visken	5 mg, 10 mg
210	propranolol	Inderal	10 mg, 20 mg, 40 mg, 60 mg, 80 mg
211	propranolol long-acting	Inderal LA	60 mg, 80 mg, 120 mg, 160 mg
212	timolol	Blocadren	5 mg, 10 mg, 20 mg
213	atenolol-chlorthalidone	Tenoretic	50/25 mg, 100/25 mg
214	bisoprolol-hydrochlorothiazide*	Ziac	2.5/6.25 mg, 5/6.25 mg, 10/6.25 mg
215	metoprolol-hydrochlorothiazide*	Lopressor HCT	50/25 mg, 100/25 mg, 100/50 mg
216	nadolol-bendroflumethiazide*	Corzide	40/5 mg, 80/5 mg
217	propranolol LA- hydrochlorothiazide*	Inderide LA	40/25 mg, 80/25 mg
218	timolol-hydrochlorothiazide*	Timolide	10/25 mg
219	Nebivolol	Bystolic	2.5 mg, 5 mg, 10 mg, 20 mg
220	metoprolol succinate	Dutoprol HCTZ	25/12.5 mg, 50/12.5 mg, 100/12.5 mg

* list specific strength of each ingredient

Alpha/Beta Blockers Class Code = 200

Code	Generic Name	Brand Names	Strengths Available
220	carvedilol	Coreg	3.125 mg, 6.25 mg, 12.5 mg, 25 mg
221	labetalol	Normodyne, Trandate	100 mg, 200 mg, 300 mg
222	carvedilol extended release	Coreg CR	10 mg, 20 mg, 40 mg, 80 mg

ACE Inhibitors – Class Code = 300

Code	Generic Name	Brand Names	Strengths Available
301	benazepril	Lotensin	5 mg, 10 mg, 20 mg, 40 mg
302	captopril	Capoten	12.5 mg, 25 mg, 50 mg, 100 mg
303	enalapril	Vasotec	2.5 mg, 5 mg, 10 mg, 20 mg
304	fosinopril	Monopril	10 mg, 20 mg, 40 mg
305	lisinopril	Zestril, Prinivil	2.5 mg, 5 mg, 10 mg, 20 mg, 30 mg, 40 mg
306	moexipril	Univasc	7.5 mg, 15 mg
307	perindopril	Aceon	2 mg, 4 mg, 8 mg
308	quinapril	Accupril	5 mg, 10 mg, 20 mg, 40 mg
309	ramipril	Altace	1.25 mg, 2.5 mg, 5 mg, 10 mg
310	trandolapril	Mavik	1 mg, 2 mg, 4 mg
311	benazepril-hydrochlorothiazide*	Lotensin HCT	5/6.25 mg, 10/12.5 mg, 20/12.5 mg, 20/25 mg
312	captopril-hydrochlorothiazide*	Capozide	25/15 mg, 25/25 mg, 50/15 mg, 50/25 mg
313	enalapril-hydrochlorothiazide*	Vaseretic	5/12.5 mg, 10/25 mg
314	fosinopril-hydrochlorothiazide*	Monopril-HCT	10/12.5 mg, 20/12.5 mg
315	lisinopril-hydrochlorothiazide*	Prinzide, Zestoretic	10/12.5 mg, 20/12.5 mg, 20/25 mg
316	moexipril-hydrochlorothiazide*	Uniretic	7.5/12.5 mg, 15/12.5 mg, 15/25 mg
317	quinapril-hydrochlorothiazide*	Accuretic	10/12.5 mg, 20/12.5 mg, 20/25 mg

* list specific strength of each ingredient

Calcium Channel Blockers – Class Code = 400

Code	Generic Name	Brand Names	Available Strengths
401	amlodipine	Norvasc	2.5 mg, 5 mg, 10 mg
402	diltiazem	Cardizem, Dilacor, Tiazac	30 mg, 60 mg, 90 mg, 120 mg, 180 mg, 240 mg, 300 mg, 360 mg, 420 mg
403	felodipine	Plendil	2.5 mg, 5 mg, 10 mg
404	isradipine	DynaCirc	2.5 mg, 5 mg, 10 mg
405	nicardipine	Cardene	20 mg, 30 mg, 45 mg, 60 mg
406	nifedipine	Adalat, Procardia	10 mg, 20 mg, 30 mg, 60 mg, 90 mg
407	nisoldipine	Sular	8.5 mg, 10 mg, 17 mg, 20 mg, 25.5 mg, 30 mg, 34 mg, 40 mg
408	verapamil	Calan, Isoptin, Verelan, Coer , Covera HS	40 mg, 80 mg, 100 mg, 120 mg, 200 mg, 180 mg, 240 mg, 300 mg, 360 mg

ACE Inhibitor/Calcium Channel Blocker Combinations Class Code = 300, 400

Code	Generic Name	Brand Names	Available Strengths
410	amlodipine/benazepril*	Lotrel	2.5/10 mg, 5/10 mg, 5/20 mg, 5/40 mg, 10/20 mg, 10/40 mg
411	enalapril/felodipine *	Lexxel	5/2.5 mg, 5/5 mg
412	trandolapril/verapamil*	Tarka	1/240 mg, 2/180 mg, 2/240 mg, 4/240 mg
413	perindopril/amlodipine	Prestalia	3.5/2.5 mg, 7/5 mg, 14/10 mg

* list specific strength of each ingredient

Calcium Channel Blocker:Angiotensin II Receptor Blocker Combination*Class Code = 400, 600*

Code	Generic Name	Brand Names	Available Strengths
420	amlodipine/valsartan*	Exforge	5/160 mg, 10/160 mg, 5/320 mg, 10/320 mg
421	amlodipine/valsartan/hydrochlorothiazide	Exforge HCT	5/160/12.5 mg, 10/160/12.5 mg, 5/160/25 mg, 10/160/25 mg, 10/320/25 mg
422	amlodipine/olmesartan	AZOR	5/20 mg, 5/40 mg, 10/20 mg, 10/40 mg
423	Telmisartan/amlodipine	Twynsta	40/5 mg, 40/10 mg, 80/5 mg, 80/10 mg

* list specific strength of each ingredient

Alpha blockers – Class Code = 500

Code	Generic Name	Brand Names	Available Strengths
501	doxazosin	Cardura	1 mg, 2 mg, 4 mg, 8 mg
502	prazosin	Minipress	1 mg, 2 mg, 5 mg
503	terazosin	Hytrin	1 mg, 2 mg, 5 mg, 10 mg
504	prazosin/polythiazide	Minizide	1/0.5 mg, 2/0.5 mg, 5/0.5 mg

Angiotensin II receptor antagonists (ARB) – Class Code = 600

Code	Generic Name	Brand Names	Available Strengths
601	candesartan	Atacand	4 mg, 8 mg, 16 mg, 32 mg
602	eprosartan	Teveten	400 mg, 600 mg
603	irbesartan	Avapro	75 mg, 150 mg, 300 mg
604	losartan	Cozaar	25 mg, 50 mg, 100 mg
605	olmesartan	Benicar	5 mg, 20 mg, 40 mg
606	telmisartan	Micardis	20 mg, 40 mg, 80 mg
607	valsartan	Diovan	40 mg, 80 mg, 160 mg, 320 mg
608	candesartan-hydrochlorothiazide	Atacand HCT	16/12.5 mg, 32/12.5 mg, 32/25 mg
609	eprosartan-hydrochlorothiazide	Teveten-HCT	600/12.5 mg, 600/25 mg
610	irbesartan-hydrochlorothiazide	Avalide	150/12.5 mg, 300/12.5 mg, 300/25 mg
611	losartan-hydrochlorothiazide	Hyzaar	50/12.5 mg, 100/12.5 mg, 100/25 mg
612	olmesartan medoxomil-hydrochlorothiazide	Benicar HCT	20/12.5 mg, 40/12.5 mg, 40/25 mg
613	telmisartan-hydrochlorothiazide	Micardis-HCT	40/12.5 mg, 80/12.5 mg, 80/25 mg
614	valsartan-hydrochlorothiazide	Diovan-HCT	80/12.5 mg, 160/12.5 mg, 160/25 mg, 320/12.5 mg, 320/25 mg
615	Azilsartan Medoxomil	Edarbi	40 mg, 80 mg

Centrally Acting Alpha 2 blockers – Class Code = 700

Code	Generic Name	Brand Names	Strengths Available
701	clonidine	Catapres	0.1 mg, 0.2 mg, 0.3 mg
702	clonidine topical patch	Catapres TTS	0.1 mg, 0.2 mg, 0.3 mg
703	guanabenz	Wytensin	4 mg, 8 mg
704	guanfacine	Tenex	1 mg, 2 mg
705	methyldopa	Aldomet	250 mg, 500 mg
706	methyldopa-hydrochlorothiazide	Aldoril	250/15 mg, 250/25 mg
707	clonidine-chlorthalidone	Clorpres	0.1/15 mg, 0.2/15 mg, 0.3/15 mg

* list specific strength of each ingredient

Peripheral Adrenergic Blocking Agents – Class Code = 800

Code	Generic Name	Brand Names	Strengths Available
801	reserpine		0.1 mg, 0.25 mg
802	reserpine-chlorthalidone	Demi-Regroton	
803	reserpine-chlorothiazide	Diupres	
804	reserpine-hydrochlorothiazide	Hydropres	0.125/25 mg, 0.125/50 mg
805	Ser Ap Es		

Vasodilators – Class Code = 900

Code	Generic Name	Brand Names	Strengths Available
901	hydralazine	Apresoline	10 mg, 25 mg, 50 mg, 100 mg
902	isosorbide dinitrate	Isordil	2.5 mg, 5 mg, 10 mg, 20 mg, 30 mg, 40 mg
903	isosorbide mononitrate	Imdur	10 mg, 20 mg, 30 mg, 60 mg, 120 mg
904	minoxidil	Loniten	2.5 mg, 10 mg
905	hydralazine-hydrochlorothiazide		25/25 mg, 50/50 mg, 100/50 mg
906	isosorbide dinitrate-hydralazine	BiDil	20/37.5 mg

* list specific strength of each ingredient

Aldosterone Receptor Blockers – Class Code = 1000

Code	Generic Name	Brand Names	Strengths Available
1001	eplerenone	Inspra	25 mg, 50 mg
1002	spironolactone	Aldactone	25 mg, 50 mg, 100 mg

* list specific strength of each ingredient

Direct Renin Inhibitor – Class Code = 2000

Code	Generic Name	Brand Names	Strengths Available
2001	aliskiren	Tekturna	150 mg, 300 mg
2002	aliskiren-hydrochlorothiazide	Tekturna HCT	150/12.5 mg, 150/25 mg, 300/12.5 mg, 300/25 mg
2003	aliskiren-valsartan	Valturna	150/160 mg, 300/320 mg

